4. MATERIALS AND METHODS

4.1 PATIENTS

The target population is patients who are naive to TNF inhibitors with moderately to severely active UC (defined as MCS of 6–12, endoscopy subscore of ≥ 2 as determined by the central reading procedure described in Section 4.5.1.4, a rectal bleeding subscore ≥ 1 , a stool frequency subscore ≥ 1 , and colonic involvement extending a minimum of 20 cm from the anal verge).

4.1.1 Inclusion Criteria

Patients must meet the following criteria for study entry:

- Able and willing to provide written informed consent
- 18–80 years of age, inclusive
- Diagnosis of UC established at least 3 months prior to Day 1 by clinical and endoscopic evidence. This diagnosis should be corroborated by histopathology conducted at any time prior to screening and documented by a histopathology report. (Note that histopathology may be performed at screening if no prior report is readily available.)
- Moderately to severely active UC as determined by an MCS of 6–12 with an endoscopic subscore ≥ 2 as determined by the central reading procedure described in Section 4.5.1.4, a rectal bleeding subscore ≥ 1 , and a stool frequency subscore ≥ 1 during the screening period (prior to Day 1). See also Section 4.5.2.1 for additional information regarding the time window

- Evidence of UC extending a minimum of 20 cm from the anal verge as determined by baseline endoscopy (flexible sigmoidoscopy or colonoscopy) performed during screening, 4–16 days prior to Day 1. See also Section 4.5.2.1 for additional information regarding the time window
- Naive to treatment with TNF inhibitors
- Patients must have had an inadequate response, loss of response, or intolerance to prior immunosuppressant and/or corticosteroid treatment

Inadequate response to, loss of response to, or intolerance to prior immunosuppressant treatment, is defined as one or more of the following:

Persistent signs and symptoms of active disease despite a history of at least one 12-week regimen of oral AZA (≥ 1.5 mg/kg) or 6-MP (≥ 0.75 mg/kg) and/or MTX (≥ 15 mg/week) within the previous 5 years

Persistent signs and symptoms of active disease despite a 6-TG level of ≥ 230 pmol/ 8×10^8 RBCs during at least one 12-week regimen of oral AZA or 6-MP at a stable or increasing dose within the previous 5 years

History of intolerance to AZA, 6-MP, or MTX (including, but not limited to, nausea/vomiting, abdominal pain, pancreatitis, LFT abnormalities, lymphopenia, TPMT genetic mutation, infection) within the previous 5 years

- Inadequate response, loss of response, or intolerance to corticosteroid treatment is defined as one or more of the following:

Steroid refractory: persistent symptoms of active disease despite treatment with at least one 4-week induction regimen that included a dose of ≥ 30 mg prednisone (oral) daily (or equivalent) for at least 2 weeks or intravenously for at least 1 week within the previous 5 years

Steroid dependent: two failed attempts to taper steroids below a dose equivalent to 10 mg prednisone (oral) daily

Steroid intolerant: history of intolerance to corticosteroids (including, but not limited to, Cushing's syndrome, osteopenia/osteoporosis, hyperglycemia, insomnia, infection) within the previous 5 years

- Any ongoing UC therapy must be at stable doses:

May be receiving oral 5-ASA compounds provided that the dose has been stable for ≥ 4 weeks immediately prior to Day 1

May be receiving oral corticosteroid therapy (prednisone at a stable dose of ≤ 30 mg a day, or equivalent steroid)

If corticosteroid therapy is ongoing or has recently been initiated, the dose has to be stable for at least 4 weeks immediately prior to Day 1. If corticosteroids are being tapered, the dose has to be stable for at least 2 weeks immediately prior to Day 1.

May be receiving budesonide therapy at a stable dose of up to 9 mg a day for ≥ 4 weeks prior to Day 1

May be receiving probiotics (e.g., Culturelle, *Saccharomyces boulardii*), provided that the dose has been stable for ≥ 2 weeks immediately prior to Day 1

May be receiving AZA, 6-MP, or MTX, provided that the dose has been stable for ≥ 8 weeks immediately prior to Day 1

- For women who are not postmenopausal (at least 12 months of non-therapy-induced amenorrhea) or surgically sterile (e.g., absence of ovaries and/or uterus): agreement to remain abstinent or use a highly effective method of contraception during the treatment period and for at least 24 weeks after the last dose of study drug (see [Appendix 3](#)).

The reliability of sexual abstinence should be evaluated in relation to the duration of the clinical trial and the preferred and usual lifestyle of the patient. Periodic abstinence (e.g., calendar, ovulation, symptothermal, or postovulation methods) and withdrawal are not acceptable methods of contraception.

- For men: agreement to remain abstinent (refrain from heterosexual intercourse) or use contraceptive measures, and agreement to refrain from donating sperm, as defined below:

With female partners of childbearing potential or pregnant female partners, men must remain abstinent or use a condom during the treatment period and for at least 24 weeks after the last dose of study drug to avoid exposing the embryo to study drug. Men must refrain from donating sperm during this same period.

The reliability of sexual abstinence should be evaluated in relation to the duration of the clinical trial and the preferred and usual lifestyle of the patient. Periodic abstinence (e.g., calendar, ovulation, symptothermal, or postovulation methods) and withdrawal are not acceptable methods of contraception.

- Must have received a colonoscopy within the past year or be willing to undergo a colonoscopy in lieu of a flexible sigmoidoscopy at screening. This colonoscopy must:

Confirm disease extent (defined as 1) left-sided colitis [up to the splenic flexure], 2) extensive colitis [beyond the splenic flexure but not involving the entire colon], and 3) pancolitis; see Section [4.5.1.4](#))

Include removal of any adenomatous polyps

Document evidence of surveillance for dysplasia for all patients with left-sided colitis of > 12 years' duration and total/extensive colitis of > 8 years duration

4.1.2 Exclusion Criteria

Patients who meet any of the following criteria will be excluded from study entry:

Exclusion Criteria Related to Inflammatory Bowel Disease

- Prior extensive colonic resection, subtotal or total colectomy, or planned surgery for UC
- Past or present ileostomy or colostomy
- Diagnosis of indeterminate colitis
- Suspicion of ischemic colitis, radiation colitis, or microscopic colitis
- Diagnosis of toxic megacolon within 12 months of initial screening visit
- Any diagnosis of Crohn's disease
- Past or present fistula or abdominal abscess
- A history or current evidence of colonic mucosal dysplasia
- Patients with any stricture (stenosis) of the colon
- Patients with history or evidence of adenomatous colonic polyps that have not been removed

Exclusion Criteria Related to Prior or Concomitant Therapy

- Any prior treatment with etrolizumab or other anti-integrin agents (including natalizumab, vedolizumab, and efalizumab)
- Any prior treatment with anti-adhesion molecules (e.g., anti-MAdCAM-1)
- Any prior treatment with rituximab
- *Any treatment with tofacitinib during screening*
- Use of IV steroids within 30 days prior to screening with the exception of a single administration of IV steroid
- Use of agents that deplete B or T cells (e.g., alemtuzumab or visilizumab) within 12 months prior to Day 1, with the exception of AZA and 6-MP
- Use of cyclosporine, tacrolimus, sirolimus, or mycophenolate mofetil (MMF) within 4 weeks prior to Day 1
- Chronic nonsteroidal anti-inflammatory drug (NSAID) use. (Note: occasional use of NSAIDs and acetaminophen [e.g., headache, arthritis, myalgias, or menstrual cramps] and aspirin up to 325 mg daily is permitted.)
- Patients who are currently using anticoagulants including, but not limited to, warfarin, heparin, enoxaparin, dabigatran, apixaban, rivaroxaban. (Note that antiplatelet agents such as aspirin up to 325 mg daily or clopidogrel are permitted.)
- Patients who have received treatment with corticosteroid enemas/suppositories and/or topical (rectal) 5-ASA preparations within 2 weeks prior to Day 1
- Apheresis (i.e., Adacolumn apheresis) within 2 weeks prior to Day 1

- Received any investigational treatment including investigational vaccines within 5 half-lives of the investigational product *or 28 days after the last dose*, whichever is greater, prior to Day 1
- History of moderate or severe allergic or anaphylactic/anaphylactoid reactions to chimeric, human, or humanized antibodies, fusion proteins, or murine proteins or hypersensitivity to etrolizumab (active drug substance) or any of the excipients (L-histidine, L-arginine, succinic acid, polysorbate 20)
- Patients administered tube feeding, defined formula diets, or parenteral alimentation/nutrition who have not discontinued these treatments ≥ 3 weeks prior to Day 1

Exclusion Criteria Related to General Safety

- Pregnant or lactating
- Lack of peripheral venous access
- Hospitalized (other than for elective reasons) during the screening period
- Inability to comply with study protocol, in the opinion of the investigator
- Significant uncontrolled comorbidity, such as cardiac (e.g., moderate to severe heart failure New York Heart Association [NYHA] Class III/IV), pulmonary, renal, hepatic, endocrine, or gastrointestinal disorders (excluding UC)
- Neurological conditions or diseases that may interfere with monitoring for PML
- History of demyelinating disease
- Clinically significant abnormalities on screening neurologic examination (PML Objective Checklist)
- Clinically significant abnormalities on the screening PML Subjective Checklist
- History of alcohol, drug, or chemical abuse ≤ 6 months prior to screening
- Conditions other than UC that could require treatment with > 10 mg/day of prednisone (or equivalent) during the course of the study
- History of cancer, including hematologic malignancy, solid tumors, and carcinoma in situ, within 5 years before screening with the following exceptions:

Local basal or squamous cell carcinoma of the skin that has been excised and is considered cured is not exclusionary.

A history of chronic myelogenous leukemia, hairy cell leukemia, melanoma, renal cell carcinoma, or Kaposi sarcoma is exclusionary, irrespective of the duration of time before screening.

History of a cervical smear indicating the presence of adenocarcinoma in situ (AIS), high-grade squamous intraepithelial lesions (HSIL), or cervical intraepithelial neoplasia (CIN) of Grade > 1 is exclusionary, irrespective of the duration of time before screening.

Exclusion Criteria Related to Infection Risk

- Congenital or acquired immune deficiency
- Patients must undergo screening for HIV and test positive for preliminary and confirmatory tests
- Positive hepatitis C virus (HCV) antibody test result, unless the patient (1) has undetectable HCV RNA levels for >6 months after completing a successful course of HCV anti-viral treatment and an undetectable HCV RNA at screening or (2) has a known history of HCV antibody positivity with a history of undetectable HCV RNA and undetectable HCV RNA at screening in the absence of history of HCV anti-viral treatment.
- Patients must undergo screening for hepatitis B virus (HBV). This includes testing for HBsAg (HBV surface antigen), anti-HBc total (HBV core antibody total), and HBV DNA (patients who test negative for these tests are eligible for this study):

Patients who test positive for surface antigen (HBsAg +) are not eligible for this study, regardless of the results of other hepatitis B tests.

Patients who test positive only for core antibody (anti-HBc +) must undergo further testing for hepatitis B DNA (HBV DNA test).

If the HBV DNA test is positive, the patient is not eligible for this study.

In the event the HBV DNA test cannot be performed, the patient is not eligible for this study.

If the HBV DNA test is negative, the patient is eligible for this study. These patients will undergo periodic monitoring for HBV DNA during the study.

- Evidence of or treatment for *Clostridium difficile* (as assessed by *C. difficile* toxin testing) within 60 days prior to Day 1 or other intestinal pathogens (as assessed by stool culture and ova and parasite evaluation) within 30 days prior to Day 1
- Evidence of or treatment for clinically significant cytomegalovirus (CMV) colitis (based on the investigator's judgment) within 60 days prior to Day 1. Laboratory confirmation of CMV from colon biopsy sample is required during screening evaluation only if clinical suspicion is high and to determine the need for CMV treatment.
- History of active or latent TB, regardless of treatment history (see Section 4.5.1.5)
 - Patients with a history of active or latent TB (based on a positive screening assay, either purified protein derivative [PPD] skin test or QuantiFERON®-TB Gold test), are not eligible for this study.
 - Patients with a chest X-ray (posteroanterior [PA] and lateral) within 3 months of Day 1 suspicious for pulmonary TB are **not** eligible for this study.
- History of recurrent opportunistic infections and/or history of severe disseminated viral infections (e.g., herpes)
- Any serious opportunistic infection within the last 6 months

- Any current or recent signs or symptoms (within 4 weeks before screening and during screening) of infection, except for the following:
 - Minor infections (e.g., common cold) that have, in the investigator's judgment, completely resolved prior to Day 1
 - Fungal infections of the nail beds
 - Oral or vaginal candidiasis that has resolved with or without treatment prior to Day 1
- Any major episode of infection requiring treatment with IV antibiotics within 8 weeks prior to screening or oral antibiotics within 4 weeks prior to screening
 - Treatment with antibiotics as adjunctive therapy for UC in the absence of documented infection is not exclusionary.
- Received a live attenuated vaccine within 4 weeks prior to Day 1
- History of organ transplant

Exclusion Criteria Related to Laboratory Values (at Screening)

- Serum creatinine >2 times upper limit of normal (ULN)
- ALT or AST >3×ULN, or alkaline phosphatase >3×ULN, or total bilirubin >2.5×ULN (unconjugated hyperbilirubinemia that is associated with known Gilbert's syndrome is not an exclusion criterion)
- Platelet count <100,000/μL
- Hemoglobin <8 g/dL
- Absolute neutrophil count <1500/μL
- Absolute lymphocyte count <500/μL

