Patients not achieving clinical response at Week 10 and patients completing the Maintenance Phase at Week 62 should enroll in Part 1 (OLE) of Study GA28951, if eligible, where they will receive open-label etrolizumab. If they do not enroll in Part 1 (OLE) of Study GA28951, they will enter the 12-week safety follow-up period of this study and then will be requested to enroll in Part 2 (SM) of Study GA28951 for 92 weeks of extended PML monitoring.

Etrolizumab—F. Hoffmann-La Roche Ltd
35/Protocol GA29102, Version 7

Clinical Study Report: etrolizumab - F. Hoffmann-La Roche Ltd
Protocol GA29102 Report Number 1099518

Study Drug Administration

The first two doses of study medication will be administered via a prefilled syringe (PFS) by a health care professional (HCP) in the clinic. The subsequent two doses will be self-administered by the patient or administered by his or her caregiver in the clinic and monitored by the HCP. If deemed appropriate by the HCP, the remaining doses of study drug, starting at Week 16, will be self-administered by the patient or administered by his or her caregiver at home Q4W (action to be taken as a result of a hypersensitivity reaction is provided in Section 5.1.5). The administration of the study medication at home by the patients or their caregivers will occur after their study assessments in the clinic setting. If necessary, patients or their HCPs may choose to continue administration of study medication in the clinic. The details of study medication administration are provided in Section 4.3.2.

Oral Corticosteroids during the Study

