4.5.2.3 Assessments at Study Completion/Early Withdrawal from Treatment Visit

The completion of study treatment period is defined as the Week 62 visit. Patients who complete the treatment medication will be asked to visit the clinic for Week 62 assessments. Eligible patients who consent to receive open-label etrolizumab in Part 1 (OLE) of Study GA28951 are to receive their first dose of open-label etrolizumab 4 weeks after their last dose of study medication in this study. On occasions where this first dose of etrolizumab in Part 1 (OLE) of Study GA28951 cannot be administered in accordance with these requirements, the first dose of etrolizumab is to be administered with a maximum delay of 2 weeks from the scheduled dosing day in Study GA28951.

If a patient leaves the study prior to Week 62, an early withdrawal from treatment visit is to be conducted at his or her next scheduled visit, including for those patients who are enrolling in Study GA28951 (OLE-SM). Assessments are specified in the Schedule of Assessments in [Appendix 1](#). Following completion of assessments at this early withdrawal from treatment visit, eligible patients are to receive their first dose of open-label etrolizumab in Part 1 (OLE) of Study GA28951 4 weeks after their last dose of study medication in this study, with a maximum delay of 2 weeks from the scheduled dosing day in Study GA28951.

At any timepoint, patients who are not eligible or who choose not to enroll in Part 1 (OLE) of Study GA28951 are to enroll in Part 2 (SM) of Study GA28951 for extended PML follow-up after completion of the 12-week safety follow-up in this study.

Patients who were treated with prohibited medication are to have their early withdrawal from treatment visit at their next scheduled visit followed by the 12-week safety follow-up phase of this study (telephone call at Week 6 and clinic visit at Week 12; see [Appendix 2](#)). Patients are to enroll in Part 2 (SM) of Study GA28951 for extended PML monitoring.

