4.5.2.3.1 Eligibility for Entry to Open-Label Extension and Safety Monitoring Study

The OLE-SM (Study GA28951) study will be conducted under a separate protocol and eligible patients as described below (also see [Table 4](#)) will need to be willing and able to provide separate informed consent to enter this study.

Note: Patients who are not eligible or who do not wish to receive open-label etrolizumab in Part 1 (OLE) of Study GA28951 will be requested to enroll in the 92-week extended PML monitoring (Part 2 [SM] of Study GA28951) after completing the 12-week safety follow-up in this study.

The following patients may be eligible to enroll in Part 1 (OLE) of Study GA28951:

- In the Induction Phase, any patients who requires initiation of an immunosuppressant (ASA, 6-MP, MTX), corticosteroid, or oral or topical 5-ASA, or increase in dose of these medications over baseline levels for treatment of worsening disease symptoms may enroll in Part 1 (OLE) of Study GA28951 after the Week 10 assessment, if eligible.
- Patients who do not achieve a clinical response at Week 10
- Patients who meet the criteria for relapse (see [Section 3.1.1.1](#) for definition) at any time between Week 10 and Week 62
- Patients who were not receiving corticosteroids at baseline and patients who have completed the steroid taper may be eligible for Part 1 (OLE) of Study GA28951 if they receive oral corticosteroids at a dose greater than 10 mg for 5 days or longer for the treatment of clinical symptoms of either UC or steroid withdrawal.
- Patients who use IV or topical corticosteroids, who use topical 5-ASA, or who initiate or escalate dose of oral 5-ASA to treat worsening symptoms of UC in the Maintenance Phase
- Patients who require initiation of or an increase in the dose of immunosuppressants during the Maintenance Phase
- All remaining patients at end of Week 62

The following patients are NOT eligible to enroll in Part 1 (OLE) of Study GA28951:

- Patients who discontinue study treatment prior to Week 10 or do not perform the Week 10 visit
- Patients who require rescue medications that are prohibited in conjunction with etrolizumab (see Section [4.3.2.2](#))
- Patients with severe hypersensitivity reactions (see Section [4.6.1.1](#)), specific malignancies, specific de novo or reactivated serious viral infections, PML, or other life-threatening infections during the study (see [Table 5](#) and Sections [4.6.1.1](#) and [5.1.5](#))

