Table 4 Eligibility for Enrollment into Part 1 (OLE) of Study GA28951 or Transfer to 12-Week Safety Follow-Up

Time Period	Rationale	May Enroll in Part 1 (OLE), if Eligible (from Week 10 Onward)	Must Transfer to 12-Week Safety Follow-Up of this Study
Day 1 to Week 10	Initiation of an immunosuppressant (AZA, 6-MP, MTX) oral or topical 5-ASA, or corticosteroid, or increase dose in these medications over baseline levels	Yes (may enroll at the 10-week timepoint)	Yes (must transfer to SFU if patient does not choose OLE)
Week 10	Did not achieve a clinical response at Week 10	Yes	
Week 10 to Week 62	Met criteria for clinical relapse (see Section 4.4.3) at any time between Week 10 and Week 62	Yes	Yes (must transfer to SFU if patient does not choose to receive study medication in Maintenance Phase or to participate in OLE)
Day 1 to Week 62	Use of oral corticosteroids at a dose greater than 10 mg for 5 days or longer for patients who were not receiving corticosteroids at baseline and patients who have completed the steroid taper	Yes	
Day 1 to Week 62	Use of IV or topical corticosteroids or oral or topical 5-ASA, or increase in dose of oral 5-ASA over baseline level	Yes	
Week 62	End of treatment period (all remaining patients)	Yes	Yes (must transfer to SFU if patient does not choose OLE)
Day 1 to Week 10	Discontinuation of study treatment or missing the Week 10 visit	No	Yes (after dosing termination visit)
Day 1 to Week 62	Patients requiring rescue medications that are prohibited (see Section 4.3.2.2)	No	
Day 1 to Week 62	Occurrence of severe hypersensitivity reactions (see Section 4.6.1.1), specific malignancies, specific de novo or reactivated serious viral infections, PML or other life-threatening infections during the study (see Table 5 and Sections 4.6.1.1 and 5.1.5)	No	

5-ASA = 5-aminosalicylic acid; 6-MP = 6-mercaptopurine; AZA = azathioprine; IV = intravenous; MTX = methotrexate; OLE = open-label extension; PML = progressive multifocal leukoencephalopathy; SFU = safety follow-up.

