4.6.1.1 Discontinuation from Study Drug

Patients must discontinue study drug if they experience any of the following:

- Pregnancy
- Anaphylaxis or other severe hypersensitivity reaction
- Develop colonic mucosal dysplasia
- Malignancy (with the exception of local and resected basal or squamous cell carcinoma of the skin) or cervical Pap test with AIS, HSIL, or CIN of Grade > 1
- Specific serious infection (see [Table 5](#) for details on serious infection):
 - Any patient who experiences a de novo or reactivated serious viral infection, such as HBV, HCV, HIV, should discontinue study medication.
 - Any patient who develops life-threatening infections during the study should discontinue study medication.
- Any medication for rescue outside defined limits of the protocol (see [Section 4.3.2](#))

Patients who discontinue study drug prematurely for the reasons listed above will be asked to return to the clinic for a study drug completion/early withdrawal from treatment visit (see Section 4.5.2.3) and will continue to undergo safety follow-up assessments for 12 weeks within this study. Patients should then enroll in Part 2 (SM) of Study GA28951 for 92 weeks of monitoring for PML (see Section 4.5.2.4). The primary reason for premature study drug discontinuation should be documented on the appropriate eCRF. Patients who discontinue study drug prematurely will not be replaced.

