- ^m Enrolled patients who are hepatitis B core antibody positive should have hepatitis B DNA measured at these timepoints.
- ⁿ Measurement of HCV RNA with use of the Amplicor assay is required when the patient has a known history of HCV antibody positivity with past documentation of undetectable HCV RNA, either with or without history of anti-viral treatment. Patients with newly diagnosed HCV antibody positivity are not eligible for this study and, therefore, do not require measurement of HCV RNA.
- ^o All samples to be collected prior to administration of etrolizumab. Serum baseline, Week 4, and blood sample (RNA Paxgene) are to be collected prior to dose of etrolizumab from all patients. All subsequent samples (serum and Paxgene whole blood) will be collected only from those who were eligible to be randomized into the Maintenance Phase.
- ^p If serum sickness or a clinically significant allergic drug reaction is suspected, Sponsor should be notified, and serum for etrolizumab level and ATAs should be drawn and sent to the central laboratory. ATA samples may also be utilized for exploratory PD assessments or assessment of drug concentrations.
- ^q Collection of sample for ATA is required at final or early withdrawal visit, unless it coincides with first visit in Part 1 of Study GA28951 (where a sample for ATA must be collected).

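### Anti-HBc-positive patients who leave before Week 12 and do not enter the open-label extension have no scheduled HBV DNA test after their first dose

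*Protocol*

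**What the plan says.** - **Commitment.** Protocol 4.1.2, under infection risk, lets in patients with a positive core antibody and a negative HBV DNA test, and adds: "These patients will undergo periodic monitoring for HBV DNA during the study".
- **Who and when.** Appendix 1, footnote m: "Enrolled patients who are hepatitis B core antibody positive should have hepatitis B DNA measured at these timepoints". It speaks of enrolled patients, not only randomized ones. The row is marked at Screening and Weeks 12, 24, 32, 44 and 62, and is blank at Weeks 0 to 10, Unscheduled and Early Withdrawal.
- **Follow-up.** Appendix 2 lists ECG, the PML examination, PD, PK and antibody serum, medication changes and adverse events. It has no HBV DNA and no chemistry.
- **Non-responders.** Section 3.1.1 says Week 10 non-responders should go to Part 1 (OLE) of GA28951 if eligible. Otherwise: "If they do not enroll in Part 1 (OLE) of Study GA28951, they will enter the 12-week safety follow-up period of this study".
- **Early leavers.** Section 4.5.2.3.1 lists among those not eligible for the OLE: "Patients who discontinue study treatment prior to Week 10 or do not perform the Week 10 visit". Table 4 sends the same group, described as "Discontinuation of study treatment or missing the Week 10 visit", to the 12-week follow-up.
- **Related rules.** Section 4.6.1.1: "Any patient who experiences a de novo or reactivated serious viral infection, such as HBV, HCV, HIV, should discontinue study medication". Section 4.5.2.3.1 also bars from the OLE patients with "specific de novo or reactivated serious viral infections, PML, or other life-threatening infections during the study".

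**The concern.** The monitoring sentence accompanies the decision to admit a group with a known reactivation risk, yet everyone who leaves before Week 12 leaves before monitoring starts. No exit visit makes up for it, because Early Withdrawal and the follow-up clinic visit are also unmarked. Section 4.5.2.4 describes the later extended monitoring in Part 2 of GA28951 as telephone checks for PML, so that does not close the gap either.

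These patients may be on azathioprine, 6-MP or methotrexate and up to 30 mg prednisone. Under Section 3.1.1.2, anyone given a prohibited agent such as a TNF or JAK inhibitor during induction must also go to follow-up. At stake is how soon a reactivation that began during or after induction would be found.

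**Working it through.** The plan gives no figure of its own here, so the check is a reading of the schedule followed by simple arithmetic.

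**1. Schedule.** Matching the Appendix 1 HBV DNA row to its 21 columns gives Screening and Weeks 12, 24, 32, 44 and 62. The PK, MCS and pMCS rows, read the same way, also have 21 columns and fall on their expected weeks. HBV DNA tests scheduled after the first dose:
- Week 62 completer: 5.
- Week 10 non-responder outside the OLE, or anyone leaving before Week 12: 0.

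**2. Age of the only result at the follow-up clinic visit.** That visit is 12 weeks after the last dose (Section 4.5.2.4). Screening tests fall 0 to 5 weeks before Day 1 (35 days, Section 4.5.2.1). Age = week of last dose + 12 + screening lead.

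| Last dose | Visit | Age of result |
|---|---|---|
| Week 0 | Week 12 | 12 to 17 weeks |
| Week 4 | Week 16 | 16 to 21 weeks |
| Week 8 | Week 20 | 20 to 25 weeks |

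Section 4.5.2.1.2 lets a re-screened patient carry over a hepatitis B result up to 6 weeks old, which raises the upper limits to 18, 22 and 26 weeks.

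For comparison, a completer's last dose is Week 60 and the follow-up visit is Week 72. The Week 62 result is then 72 − 62 = 10 weeks old. Intervals between scheduled tests after baseline are 12 (Weeks 12–24), 8 (24–32), 12 (32–44) and 18 weeks (44–62).

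**3. How many patients.** On the protocol's 60% response assumption, non-responders number 350 × (1 − 0.60) = 140. Those affected are 140 × s × p, where s is the share not entering the OLE and p is core antibody prevalence. Neither is in the documents, so both are assumed:
- s = 10%, p = 1%: 140 × 0.10 × 0.01 = 0.14
- s = 25%, p = 5%: 140 × 0.25 × 0.05 = 1.75
- s = 50%, p = 10%: 140 × 0.50 × 0.10 = 7

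Core-antibody-positive patients who stop before Week 10 come on top; the documents give no rate for them.

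**4. What cover exists.** Chemistry, including ALT and AST, is scheduled at Week 10 and Early Withdrawal. It is done if indicated at unscheduled visits (Section 4.5.2.5), and liver tests are done as clinically indicated (Table 5). In the safety follow-up all laboratory work-up is as indicated.

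**The case against.** The strongest reply is that the documents do not contradict each other. Section 4.1.2 promises periodic monitoring without an interval or a first date, and footnote m supplies the dates. A first test at Week 12 comes 12 to 17 weeks after screening, within the 18-week interval already accepted for treated patients. That stands for anyone who reaches Week 12. It does not help a patient who leaves earlier and is never tested again.

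A reader might infer that these patients miss a decision to stop drug or to bar OLE entry. The documents do not support that. Patients who stop before Week 10 are already off drug and barred from the OLE, and non-responders who stay out of it receive no more drug. The stopping rule also concerns serious viral infection and sets no HBV DNA threshold. For non-responders who do enter the OLE, a Week 10 result would inform the bar, but whether a gap exists for them depends on the GA28951 protocol, which is not available here.

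A reader might also take all 140 expected non-responders as unmonitored. Only the core-antibody-positive ones are due HBV DNA monitoring, and OLE entry is the default route.

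Finally, there is further indirect cover: potential drug-induced liver injury meeting Hy's Law is reportable within 24 hours, significant hepatic events are to be evaluated promptly, the infectious agent is to be sought in serious infections, adverse events are collected at both follow-up contacts, and the protocol reports no increase in serious or opportunistic infections in Phases I and II. This lowers the severity, but none of it is the HBV DNA monitoring that Section 4.1.2 describes.

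**Conclusion.** The gap is real and narrow. Followed exactly, the plan gives no scheduled HBV DNA result after first dose to core-antibody-positive patients who leave before Week 12 and do not enter the OLE. For a non-responder with three doses, the only result is 20 to 25 weeks old at the follow-up clinic visit (26 with a carried-over test). The harm is delayed detection after drug has stopped.

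The reading of the schedule is firm. The count is not: 0.14 to 7 non-responders rests on the assumed ranges for s and p and on the protocol's 60% response rate, and early leavers are additional. No endpoint or analysis is touched. This is a low-severity, inexpensive safety improvement.

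**What to change.** For core-antibody-positive patients only:

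- In Appendix 1, mark HBV DNA at Week 10 (added, or moved from Week 12) and at Early Withdrawal.
- In Appendix 2, mark HBV DNA at the Week 12/Early Termination visit.
- Make the same Appendix 1 edit in the copy of the schedule in SAP Appendix 2.

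Week 10 and Early Withdrawal already draw blood for hematology, chemistry and CRP, and the follow-up visit draws PK, PD and antibody serum. No visit or venepuncture is added. A Week 10 sample would also precede the first OLE dose, which is due in "Part 1 (OLE) of Study GA28951 4 weeks after their last dose of study medication in this study", that is Week 8 + 4 = Week 12.

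If the Week 12 test is moved, the next interval becomes 24 − 10 = 14 weeks, still under the 18 weeks already scheduled. The added load is then at most two assays per patient (Week 10 or Early Withdrawal, plus the follow-up visit). The downside is a few extra central-laboratory assays.
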